## 9.6 Data management

R language (<http://www.r-project.org>) will be used for data management for creating the analysis database and in statistical analysis for creating tabulations and graphics as well as in all statistical modelling. R language is described in a detailed report "R: Regulatory Compliance and Validation Issues: A Guidance Document for the Use of R in Regulated Clinical Trial Environments" ([www.r-project.org/doc/R-FDA.pdf](http://www.r-project.org/doc/R-FDA.pdf)). Full audit trail, starting from raw data obtained from register holders and ending with the creation of statistical tables and graphs in reports, will be maintained. Source code of data management and data analyses is kept for inspection for five years after publication of results. The study may be inspected by the sponsors' independent representative(s) or by competent authorities.

All study data and supporting documents will be retained for ten years after the completion of the study report. At the end of that period EPID Research shall request further instructions from the MAHs. EPID Research shall not destroy any relevant material related to the study without prior approval from all MAHs involved in the study. As the register holder of the study register EPID Research is in charge of archiving and deleting the data. Secure archives will be maintained for the orderly storage and retrieval of all study related material. An index shall be prepared to identify the archived contents and their location. Access to the archives will be controlled and limited to authorised personnel only. Access to the study data cannot be given to any third parties, and the study data cannot be used for other purposes than prescribed in this protocol. All requests to use the study data for other purposes than mentioned in this study protocol must be subjected to appropriate data permit processes.

## 9.7 Data analysis

The individual patient-level data from each country will be pooled into a single dataset and analyses will be done using the pooled dataset.

EPID Research will perform all statistical analyses by using the R programming language (<http://www.r-project.org>). Described below is the analysis strategy. A separate detailed statistical analysis plan will be written after approval of the study protocol.

### 9.7.1 Population description

The study population consists of pregnant women with MS. A pregnancy event refers to terminations of pregnancy, spontaneous abortions, ectopic pregnancies, stillbirths and live births. The pregnancy event is considered as the experimental unit in this study. One woman may have several pregnancy events during the study period and all pregnancy events are included in the analysis.

The characteristics of all pregnancies are to be described with n, mean, median, standard deviation (SD), minimum, maximum and inter-quartile range for continuous variables and with n and percentage (%) for categorical variables. These population characteristics are to be presented for each study cohort separately and also for the whole study population. The following variables are to be included in the population description as available from the different countries:

- Country, university hospital district,
- Duration of MS treatment,
- Time since MS diagnosis,
- Year of pregnancy outcome,
- Maternal age at LMP,
- Pre-pregnancy maternal weight,
- Pre-pregnancy maternal BMI,
- Any chronic diseases during or before pregnancy,
- Exposure to any teratogenic medications (including steroids) during or before pregnancy,
- Number of previous pregnancies,
- Number of previous abortions,
- Smoking status during pregnancy and
- Number of foetuses in pregnancy (single, multiple).

Confounding factors and effect modifiers will be taken into account in the analyses according to availability and available time period from each register source.

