With these sample sizes and baseline outcome prevalence, the minimum detectable effect size between the MS women exposed to IFN- $\beta$  only (cohort 1) vs. MS women unexposed to any MSDMDs (cohort 3) is 1.72 in terms of RR using 80% power and a 5% two-sided significance level. If the background prevalence calculated among MS pregnancies unexposed to any MSDMD's would be closer to that in the whole population, e.g. 6%, 5%, 4% or 3%, the respective minimum detectable effect sizes would be 1.81, 1.91, 2.04, and 2.23. Regarding the comparison of a composite serious adverse pregnancy outcome between women with MS exposed to IFN- $\beta$  only (cohort 1) vs. unexposed to IFN- $\beta$  regardless of exposure to other MSDMDs (cohort 4), the minimum detectable effect size (RR) is approximately 1.77. Regarding the comparison of the composite serious adverse pregnancy outcome between women with MS exposed to IFN- $\beta$ s regardless of exposure to other MSDMDs (cohort 2) vs. unexposed to any MSDMD (cohort 3), the minimum detectable effect size (RR) is approximately 1.66.

The sample size calculations were performed using the `bpower` function of the R programming language (<http://www.r-project.org>).

**Table 5: The estimated numbers of all MS pregnancies and MS pregnancies unexposed to IFN- $\beta$ s available for the study during the study period by country.**

Country and study period		ALL MS Pregnancies	MS Pregnancies unexposed to IFN- $\beta$ s 
Country	Study period	Number of pregnancies	Number of pregnancies
Finland	1 Jan 1996 – 31 Dec 2014	777 	606 
Sweden	1 Jul 2005 – 31 Dec 2014	482 	376 
Norway	1 Jan 2004 – 31 Dec 2014	412 	321 
TOTAL		1671	1303

1) Estimated as 433 from time period 1 Jan 1996 – 31 Dec 2010 plus 4\*86 MS pregnancies from four additional years 2011 – 2014 where 86 denotes the number of MS pregnancies in 2010

2) Estimated as 329 MS births from Jul 2005 – 31 Dec 2011 plus (329 / 6.5) MS births from three additional years 2012 – 2014.

3) Estimated as 330 MS births from 1 Jan 2004 – 31 Dec 2014 divided by (1-0.2) where 0.2 denotes the estimated abortion prevalence

4) Estimated as the number of ALL MS PREGNANCIES x 78% where 78% denotes the estimated proportion of MS pregnancies unexposed to IFN- $\beta$  regardless of exposure to other MSDMDs

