### 9.7.3 Analysis of primary objectives

With regard to objective #1, the descriptive statistics including the number of events (n) and prevalence (%) will be presented for each pregnancy outcome (i.e. serious adverse pregnancy outcome, elective TOPFA, MCA, stillbirth, and live birth) in each study cohort separately and also for the whole study population. Information on live births, stillbirths and TOPFAs will be included in the analyses of MCA, as approximately 10% of MCAs are detected in foetuses of TOPFA.

With regard to objective #2, the prevalence of the serious adverse pregnancy outcomes will be compared between the study cohorts using log-binomial regression. Two models, base and adjusted, will be used in these comparisons. The base model will be adjusted for the following design variables and *a priori* likely confounders: country, year of pregnancy outcome, maternal age at LMP, number of previous pregnancies, any chronic diseases, and exposure to any teratogenic medications including steroids.

The adjusted model will be built using a variable selection procedure (Bursac et al. 2008). Candidate covariates for the adjusted model will be those in the base model and the following additional ones: university hospital district, pre-pregnancy weight, pre-pregnancy BMI, number of previous abortions, smoking status during pregnancy, number of foetuses in pregnancy (single vs. multiple), time since MS diagnosis and duration of MS treatment as available in the data sources. Variable selection starts by applying first the unadjusted model and proceeds as follows:

1. Each candidate covariate will be considered a potential confounder if the univariate association between the covariate and the serious adverse pregnancy outcome, tested with the Wald test for logistic regression with *P*-value cut-point of 0.25.
2. All candidate covariates identified as potential confounders in step 1 will be added simultaneously to the model. After this, additional covariates not identified as potential confounders in step 1 will be added to the model one at a time and the model fit comparing each null vs alternative model will be assessed by the likelihood-ratio test. Variables in the alternate model will be retained at a likelihood ratio test of *P*-value <0.1.

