3. An iterative process of reducing the model in step 2 will be performed by refitting and verifying model fit comparing null vs. alternative models by likelihood ratio test of *P*-value <0.1 to determine the main effects model.
4. Model fit results and the effect of adding and removing variables in step 2 and step 3 will be reported at each step. If there are a low number of outcomes identified, the final adjusted model will be limited to a covariate-outcome ratio of 1 covariate: 10 outcomes to avoid over-adjustment. If the number of covariates is higher than the covariate-outcome ratio allows, then the covariates with least significant effect to the model fit will be omitted.

Comparisons will be made separately for different study cohorts: i) one comparison will be made between women with MS exposed to IFN- $\beta$  only (cohort 1) vs. unexposed to any MSDMDs (cohort 3) and ii) another between women with MS exposed to IFN- $\beta$  only (cohort 1) vs. unexposed to IFN- $\beta$  regardless of exposure to other MSDMDs (cohort 4). The RR estimates with 95% CIs and associated *p*-values will be reported for these comparisons and for all relevant covariates used in the model.

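### Every pregnancy of a woman is analysed as a separate unit with no allowance for within-woman correlation, so the CIs, p-values and minimum detectable RRs assume independence; the effect is probably modest.

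*Protocol*

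**What the plan says.** Protocol section 9.7.1 sets the unit: "The pregnancy event is considered as the experimental unit in this study". It then states: "One woman may have several pregnancy events during the study period and all pregnancy events are included in the analysis".

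Section 9.7.3 says that the prevalence of the serious adverse outcome "will be compared between the study cohorts using log-binomial regression". Covariates are screened one at a time, "tested with the Wald test for logistic regression with" a cut-point of 0.25. They are then kept or dropped by likelihood-ratio test: "Variables in the alternate model will be retained at a likelihood ratio test of" P < 0.1. The reported results are given as "The RR estimates with 95% CIs and associated" p-values. Section 9.7.4 carries the same approach to objective 3 and compares the outcomes of objective 4 between cohorts.

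Section 9.5 gives minimum detectable RRs of 1.72 (cohort 1 vs 3), 1.77 (cohort 1 vs 4) and 1.66 (cohort 2 vs 3). The first is stated as "using 80% power and a 5% two-sided significance level". The inputs are pregnancy counts, and "The sample size calculations were performed using the" R function bpower.

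No cluster term, GEE, random effect, robust variance or one-pregnancy-per-woman analysis appears in 9.7.1–9.7.8 or in the limitations in 9.9. Section 9.7 defers detail to a statistical analysis plan that is not at hand.

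**The concern.** The study periods are 19 years in Finland, 9.5 in Sweden and 11 in Norway, and the protocol itself expects repeat pregnancies. Two pregnancies of one woman share her genetics, illness and health care, so their outcomes may be correlated, and her interferon use may be similar in both. A log-binomial likelihood that treats the pregnancies as independent then misstates the standard error of the RR.

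The number of previous pregnancies and of previous abortions are candidate covariates. They adjust the mean but leave an independence-based variance as it is. A woman can also contribute one pregnancy to each side of a comparison, so the two cohorts are not independent samples.

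At stake are the error bars on the primary safety comparisons of a study requested by the regulator, and the power statement in 9.5, which section 9.9 relies on when it says that the study has been powered for these comparisons.

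**Working it through.** **1. Reproduce the plan's figures.** Inputs from 9.5: cohort 1 = 294, cohort 2 = 368, cohort 3 = 1270 and cohort 4 = 1303 pregnancies; baseline 24/331 = 7.25% (cohort 3) and 6.5% (cohort 4); two-sided 5%, 80% power.

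For two independent binomials with pooled variance under the null:

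z = [(p1 − p0) − 1.96·√(p̄(1−p̄)(1/n1 + 1/n0))] / √(p1(1−p1)/n1 + p0(1−p0)/n0), with power = Φ(z).

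Cohort 1 vs 3 at RR 1.72: p0 = 0.0725, p1 = 0.1247, p̄ = 0.0823. The null SE is 0.01779 and the alternative SE 0.02060. So z = (0.0522 − 1.96 × 0.01779)/0.02060 = 0.842, and power is 80.0%.

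| Comparison | Stated | Independent pregnancies |
|---|---|---|
| 1 vs 3, 24/331 | 1.72 | 1.720 |
| 1 vs 4, 6.5% | 1.77 | 1.767 |
| 2 vs 3, 24/331 | 1.66 | 1.656 |
| 1 vs 3 at 6 / 5 / 4 / 3% | 1.81 / 1.91 / 2.04 / 2.23 | 1.81 / 1.90 / 2.03 / 2.23 |

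All agree to about 0.01 with no design effect, so the stated figures hold no allowance for repeat pregnancies.

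**2. Add a design effect.** The protocol gives neither the mean number of pregnancies per woman (m) nor the intra-woman correlation (ICC), so both are assumed. DEFF = 1 + (m − 1) × ICC, and each cohort size is divided by DEFF. This treats every woman as staying in one cohort, which is the unfavourable case. Cohort 1 vs 3 at a 7.3% baseline (starting point 1.717, power 80.3% at RR 1.72):

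| m | ICC | DEFF | Minimum detectable RR | Power at RR 1.72 | Actual two-sided error of a naive 5% test |
|---|---|---|---|---|---|
| 1.3 | 0.05 | 1.015 | 1.72 | 79.7% | 5.2% |
| 1.3 | 0.20 | 1.06 | 1.74 | 78.2% | 5.7% |
| 1.5 | 0.10 | 1.05 | 1.74 | 78.5% | 5.6% |
| 1.5 | 0.20 | 1.10 | 1.76 | 76.8% | 6.2% |
| 2.0 | 0.10 | 1.10 | 1.76 | 76.8% | 6.2% |
| 2.0 | 0.20 | 1.20 | 1.79 | 73.6% | 7.4% |

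The error column is 2·P(Z > 1.96/√DEFF). In the last row the CIs on the log RR should be √1.20 = 1.095 times as wide. There, cohort 1 vs 4 moves from 1.77 to 1.85, and cohort 2 vs 3 from 1.65 to 1.72 (both at the 7.3% or 6.5% baseline).

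**3. Let women change cohort.** Section 9.4 defines exposure for each pregnancy, so step 2 is an upper case. A null simulation used 1,564 pregnancies (294 + 1270), beta-binomial outcomes at 7.3%, a mean of 1.35 or 1.65 pregnancies per woman, ICC 0.05–0.20 and 4,000 replicates per setting:

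| Exposure across a woman's pregnancies | True / naive variance of log RR | Naive two-sided error |
|---|---|---|
| Varies freely | 0.98–1.04 | 4.2–4.9% |
| Correlation 0.5 | 1.03–1.13 | 4.8–5.7% |
| Fixed per woman | 1.02–1.20 | 4.8–6.7% |

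The Monte Carlo standard error near 5% is √(0.05 × 0.95/4000) = 0.34 percentage points. A cluster-robust variance gave 4.2–5.4% across all settings.

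**The case against.** **The SAP could still settle it.** Section 9.7 calls itself a strategy and promises a detailed plan, and the variance estimator for a named model is often left there. The protocol never says that the pregnancies are independent, and a sandwich variance on the final model would contradict nothing in the text. This stands in part: a reader might infer that every reported CI and p-value will be wrong, and the protocol alone does not show that. Two elements are nevertheless fixed here. The covariate selection relies on likelihood-ratio tests, which need a full likelihood and, as written, one for independent pregnancies; a robust variance added only at the end would leave those steps untouched. The minimum detectable RRs are the protocol's own and carry no design effect, whatever the SAP adds.

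**The effect may be nil.** This stands as a limit on size. A reader might infer a clear and general inflation of the error rate, to 8% or so, but that needs every woman to stay in one cohort together with assumed inputs at the far end. An ICC of 0.20 at 7.3% implies a recurrence risk of 0.073 + 0.20 × 0.927 = 25.8%, about 3.5-fold, for a composite of different events, and nothing in the protocol supports so high a value. The clusters may also be small: the 19-year window is Finland's only, and the denominators in Table 6 for the primary outcome leave out spontaneous abortions and ectopic pregnancies.

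**The shift in detectable RR is minor.** Also true. Section 9.5 already shows 1.81–2.23 for lower baselines, and the study size is set by the registers, so no recruitment decision turns on it.

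**Infant-level outcomes.** One might want the same correction there, but objective 6 is descriptive (9.7.5, Table 7), with no CIs or tests to correct.

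**Conclusion.** The point holds, at modest size. As the protocol is written, inference for the cohort comparisons rests on an independence assumption that its own choice of unit does not meet, and the power statement in 9.5 shares that assumption.

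How far this matters depends on pregnancies per woman, the intra-woman correlation of outcomes, and how stable exposure is across a woman's pregnancies. None of these is in the protocol. Over the assumed ranges the consequence runs from essentially none to a variance about 20% too small. The RR point estimates are not called into question. The direction and size cannot be settled before the data are seen, which is the reason to fix the variance method in advance.

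**What to change.** - **Section 9.7.3, by reference in 9.7.4:** state that all cohort comparisons (objectives 2–4) use a log-link model with robust variance clustered on the mother's study ID, for example log-binomial GEE, or Poisson with an independence working correlation.
- **Covariate selection:** replace the likelihood-ratio tests with cluster-robust Wald tests, and use the same variance in the univariate screen.
- **Section 9.7.6:** add a sensitivity analysis with one pregnancy per woman.
- **Section 9.5:** state that the minimum detectable RRs assume independent pregnancies, and show them over an assumed design-effect range such as 1.0–1.2. For cohort 1 vs 3 that gives about 1.72 to 1.79.

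No change is needed for objective 6. The cost is a few sentences and no new data, because section 9.3.3 already gives each person one study ID. CIs may be slightly wider and the stated detectable RR slightly less favourable.

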### 9.7.2 Denominators used for different pregnancy outcomes

The denominator used for the calculation of the descriptive statistics and prevalence of specific pregnancy outcomes in each study cohort varies by pregnancy outcome. Table 6 below describes how the denominators are defined for each pregnancy outcome.

**Table 6: Denominators used for calculation of the descriptive statistics and prevalence of pregnancy outcomes in each study cohort.**

Pregnancy outcome	Denominator used in each study cohort
Serious adverse pregnancy outcome	Number of elective terminations + number of births (still or live)
Elective TOPFA or other reasons	Number of elective terminations + number of births (still or live)
Still births	Number of elective terminations + number of births (still or live)
Live births	Number of elective terminations + number of births (still or live)
MCA	Number of elective terminations + number of births (still or live)
MCA in live births	Number of live births
Mode of delivery (CS/vaginal)	Number of live births, separately for single and multiple pregnancies
Preterm birth	Number of live births, separately for single and multiple pregnancies
Birth weight, LBW and birth weight, head circumference for gestational age	Number of live births, separately for single and multiple pregnancies
Sex of the newborn	Number of live births, separately for single and multiple pregnancies
Head circumference, low head circumference	Number of full-term live births, separately for single and multiple pregnancies
Apgar scores	Number of full-term live births, separately for single and multiple pregnancies
Ectopic pregnancies	Number of all pregnancy events
Spontaneous abortions	Number of all pregnancy events
Defect cases	Number of elective terminations + number of births (still or live)

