## 2 Terminology

**Birth** A process resulting in a foetus or a child (one or more,  $\geq 1$ ) of at least 22+0 gestational weeks (GW) ( $\geq 22+0$  GW) or weighing at least 500 grams ( $\geq 500$  g) being born by vaginal delivery or by caesarean section (CS). The process of a child being born alive is always a birth.

**Birth weight adjusted for gestational age** is defined according to the gestational age and sex-specific national standards in each country (FIN: Sankilampi et al. 2013). Average for Gestational Age (AGA) is used as reference outcome in relation to Small for Gestational Age (SGA) and Large for Gestational Age (LGA).

**Defect cases:** Cases where 3 or more minor anomalies were detected in the same child.

**Gestational age at birth** is a measure of the age of a pregnancy at birth where the origin is the first day of the woman's last normal menstrual period. Preterm birth refers to gestational age less than 37 GW.

**Induced abortion / elective termination of pregnancy** is artificially induced termination of pregnancy which does not comply with the definition of a birth and which leads to the death of one or more foetus ( $\geq 1$ ) and in which there is no indication of intrauterine foetal death before the termination.

**Live birth** is birth of a child that, irrespective of the duration of the pregnancy, breathes or shows any other evidence of life, such as beating of the heart, pulsation of the umbilical cord or movement of the voluntary muscles, whether or not the placenta is attached or the umbilical cord has been cut.

**Major congenital anomaly (MCA)** refers to a major congenital / foetal structural anomaly, chromosomal defect, teratoma and congenital hypothyroidism involved in a birth, an elective termination of pregnancy for severe MCA, or in a spontaneous abortion. MCAs do not include hereditary diseases and other diseases not associated with congenital anomalies, dysfunction of organs or tissues, developmental disabilities, congenital infections, isolated minor dysmorphic features, normal variations and common less significant congenital anomalies.

**Pregnancy event** refers to terminations of pregnancy, spontaneous abortions, ectopic pregnancies, stillbirths and live births.

**Serious adverse pregnancy outcome** is defined as a composite endpoint of pregnancy including elective termination of pregnancy due to foetal anomaly (TOPFA), MCA or stillbirth.

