### Elective terminations of pregnancy

Information on TOPFA and abortions due to other reasons will be obtained from the DPP (FIN) and MBR (NOR). The Finnish Abortion Register, which is the data source for the DPP regarding pregnancy terminations, collects data on all terminations performed in FIN since 1977. The national abortion legislation requires permission with a legal indication for terminating a pregnancy. The data of the Abortion Register are obtained from hospitals and Valvira. The information is completed with information from the national Hospital Discharge Register. More than 99% of all elective TOPs (regardless of reason of the termination (maternal social or health related, foetal related health) registered in hospital records are included in the Abortion Register (Gissler et al. 1995, Gissler et al. 1996). In NOR, abortions are included in the MBR from 12 GW onwards. SWE does not have a register on abortions.

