- Information will be obtained from the DPP (FIN) and MBR (SWE, NOR). The Finnish DPP and Norwegian MBR include information on all stillbirths of fetuses with a birth weight of at least 500 g or with a gestational age of at least 22+0 GW. The Swedish MBR includes data on stillbirths after 28 GW.

Live Birth (P):

- Information on live births will be obtained from the DPP (FIN) and MBR (SWE, NOR)

MCAs (P):

- Information will be obtained from the DPP (FIN), Patient Register (SWE) and MBR (SWE, NOR). The study will concentrate on MCAs. These outcomes are registered according to ICD-9 classification into 25 groups (ICD-codes 740-759). Minor anomalies will principally be excluded according to the European Surveillance of Congenital Anomalies (EUROCAT).

Defect cases (E):

- Information will be obtained from the DPP (FIN), Patient Register (SWE) and MBR (SWE, NOR). Defect cases with 3 or more minor anomalies will be defined according to the European Surveillance of Congenital Anomalies (EUROCAT).

Serious adverse pregnancy outcome (P):

- A composite endpoint including presence of elective TOPFA, MCA or stillbirth.

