### **Study power**

The primary comparisons in this study will be performed between MS patients exposed to IFN- $\beta$  only vs. unexposed to any MSDMDs and also between women with MS exposed to IFN- $\beta$  only vs. unexposed to IFN- $\beta$  (regardless of exposure to other MSDMDs) and the study has been powered for these comparisons. The secondary objectives will also include comparisons between women with MS exposed to IFN- $\beta$  regardless of exposure to other MSDMDs vs. unexposed to any MSDMDs which will also be sufficiently powered. However, the study is not powered for comparisons made using individual pregnancy outcomes or for comparisons that only employ a subset of the cohorts in the primary comparisons.

In the power calculations, the anticipated background prevalence of serious adverse pregnancy outcomes was based on the Finnish feasibility data. Because the availability of data regarding the serious adverse pregnancy outcome varies between countries (mainly, elective termination not available in Sweden), the observed overall prevalence of serious adverse pregnancy outcomes in all of the Nordic countries might be smaller than anticipated. However, as presented in the power calculations, if the prevalence of the serious adverse pregnancy outcome is above 3%, the minimum detectable effect size is still below 2.5 (RR).

In addition, to remove any bias from Sweden, a sensitivity analysis is being done on MCAs for the Norwegian and the Finnish data including pregnancy terminations, stillbirths and live births, and another analysis including live births only.

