**Information on elective terminations, spontaneous abortions and stillbirths**

Information on elective TOPFA is not available from SWE, while in NOR information on pregnancy terminations is available only from GW 12 onwards. Furthermore, information on spontaneous abortions is incomplete in this study, as only women treated in hospitals due to spontaneous abortions are included in the data. Usually spontaneous abortions are in the early pregnancy and women may not even know yet about the pregnancy. Therefore estimates based on hospital records lead to underestimation of the actual number of spontaneous abortions. However, it is expected, but not certain, that the underestimation of spontaneous abortions would be comparable across cohorts. Therefore, any differences observed between cohorts are likely to be due to the differences in cohort exposure. As noted in section 9.7.2, the denominator for the prevalence of MCAs includes the number of elective terminations and the number of births (still or live). Because data on elective terminations are not available in SWE, the prevalence of MCAs will be calculated first in the data from FIN and NOR. The prevalence of MCAs will then be re-calculated to include MCAs identified from SWE. However, the denominator for this prevalence will exclude the elective TOPFAs identified from FIN and NOR.

Because information on elective pregnancy terminations is not available from SWE, analyses on MCAs will be calculated including TOPFA with Finnish and Norwegian data and for births without TOPFA including data from all three countries.

Information on pregnancy terminations is available from GW 12 onwards from the Norwegian data, and therefore, information on early pregnancy terminations conducted before GW 12 could result in incomplete data. Therefore we will conduct separate analyses by trimesters on pregnancy terminations.

Information on stillbirths is available from GW 28 onwards from the Swedish data. Country-specific prevalence rates will be estimated for outcomes, where stillbirths are included as nominator, or denominator.

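### Table 6 counts terminations that can never be events in the denominator of the composite, MCA and stillbirth, and the planned workaround covers MCA only, not the primary composite

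*Protocol*

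**What the plan says.** **Denominator.** Table 6 in section 9.7.2 assigns the serious adverse pregnancy outcome, stillbirth, MCA and defect cases the denominator "Number of elective terminations + number of births (still or live"), with no restriction by reason for termination.

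**Numerator.** Section 9.4 defines the primary outcome as "A composite endpoint including presence of elective TOPFA, MCA or stillbirth". Under section 2, a termination counts towards MCA only if it is "an elective termination of pregnancy for severe MCA".

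**Capture** (section 9.3.2.2, elective terminations):
- Finland: "More than 99% of all elective TOPs" in hospital records are in the abortion register, whatever the reason.
- Norway: "In NOR, abortions are included in the MBR from 12 GW onwards".
- Sweden: "SWE does not have a register on abortions".

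**Analysis.** Data from the three countries are pooled (section 9.7). Country is a fixed term in the base log-binomial model (section 9.7.3). That section also says that MCA analyses draw on live births, stillbirths and TOPFAs, which is narrower than Table 6.

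**Workarounds.** Under the study power heading in section 9.9, the plan states that "to remove any bias from Sweden, a sensitivity analysis is being done on MCAs for the Norwegian and the Finnish data". Under the heading on elective terminations in the same section, MCA prevalence is first calculated in Finland and Norway and then recalculated with Sweden, where "the denominator for this prevalence will exclude the elective TOPFAs identified from FIN and NOR". The next paragraph describes the three-country MCA analysis as one on births with TOPFA left out. Neither place provides a matching analysis for the composite.

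**The concern.** A termination for social or maternal reasons enters the denominator of the primary endpoint and can never enter its numerator. How many such pregnancies are counted depends on each country's register.

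Two things are at stake. The first is the prevalence estimates in primary objective 1, including the background prevalence requested by the CHMP. A pooled figure is lowered by non-event terminations in Finland, less so in Norway and not at all in Sweden, so it is not one defined quantity.

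The second is the primary RR. If women exposed to IFN-β end pregnancies for non-foetal reasons at a different rate from unexposed women, the two cohorts' prevalences are scaled by different factors. The protocol makes a difference plausible without fixing its sign. Section 7 says a woman who conceives on treatment should be told of possible hazards, which could raise terminations among the exposed. Section 9.4 counts purchases at any time in pregnancy as exposure, so a pregnancy that ends early has less time to become exposed, which pushes the other way. In a safety study, attenuation is the more troubling direction.

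**Working it through.** **1. The plan's own figure.** Section 9.5 gives 294 pregnancies in cohort 1, 1270 in cohort 3, a baseline of 7.3% (24/331), 80% power and a two-sided 5% level. The minimum detectable RR solves

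p1 − p0 = 1.96·√[p̄(1−p̄)(1/n0 + 1/n1)] + 0.84·√[p0(1−p0)/n0 + p1(1−p1)/n1], with p1 = RR·p0 and p̄ the pooled proportion.

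The result is 1.717 at 7.3% and 1.720 at 24/331. The stated 1.72 is reproduced.

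**2. Effect of the denominator within one country.** Let t1 and t0 be the shares of the Table 6 denominator that are non-foetal terminations, exposed and unexposed. Each observed prevalence equals the prevalence per births plus TOPFA times (1 − t), so

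observed RR = true RR × (1 − t1)/(1 − t0).

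If t1 = t0 the factor is 1, whatever the capture.

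**3. Unequal capture alone.** Assume shares of 20% in Finland, 5% in Norway and 0 in Sweden, equal by exposure, with assumed prevalences of 8.5%, 6% and 5%. A log-binomial model with country, fitted to expected counts, returns 1.72 for a true 1.72 and 1.00 for a null. If the exposed fraction also differs by country (22% in Finland, 15% elsewhere), the crude RR is 1.77 but the country-adjusted RR is still 1.72.

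**4. Capture plus a difference by exposure.** The documents give no termination rate by exposure or reason, so these shares are assumptions: Finland t0 = 10% and t1 = 15% to 25%; Norway a quarter of each; Sweden 0.

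Country factors:
- Finland: 0.85/0.90 = 0.944 to 0.75/0.90 = 0.833
- Norway: 0.9625/0.975 = 0.987 to 0.9375/0.975 = 0.962
- Sweden: 1

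Weights are Table 5 sizes times the prevalences in step 3: 777 × 0.085 = 66.0, 412 × 0.06 = 24.7 and 482 × 0.05 = 24.1. These are shares of 0.575, 0.215 and 0.210.

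- t1 = 15%: 0.575 × 0.944 + 0.215 × 0.987 + 0.210 = 0.965, and 0.965 × 1.72 = 1.66
- t1 = 25%: 0.575 × 0.833 + 0.215 × 0.962 + 0.210 = 0.896, and 0.896 × 1.72 = 1.54

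The fitted country-adjusted model agrees to within about 0.01: roughly 1.66–1.54 for a true 1.72, and 0.96–0.89 for a null.

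**5. The other direction.** With t1 = 5% in Finland (factor 0.95/0.90 = 1.056) and 1.25% in Norway (0.9875/0.975 = 1.013), the average is 0.575 × 1.056 + 0.215 × 1.013 + 0.210 = 1.035, and 1.72 appears as 1.78.

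**6. Effect of the fix on detectable effect.** Removing 5% to 20% of the denominator equally in both cohorts raises the baseline from 7.3% to 7.7%–9.1% (0.073/0.95 to 0.073/0.80). The minimum detectable RR moves from 1.717 to 1.715–1.707.

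Restricting to Finland and Norway keeps (777 + 412)/1671 = 71% of pregnancies. That is about 209 exposed and 904 unexposed if the exposure split is the same everywhere. At a 7.3% baseline, the formula in step 1 gives about 1.87.

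**7. The two statements on MCA in section 9.9.** Taken literally, the first removes only TOPFAs, so Finnish and Norwegian terminations for other reasons stay in a denominator to which Sweden contributes none. The second describes an analysis of births. They define different denominators for the same analysis.

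**The case against.** A reader might infer that uneven registration by itself dilutes the pooled primary RR. It does not: within a country both cohorts are scaled alike, and the base model adjusts for country. Nor do the documents show that the RR is diluted at all. They report no termination rate by exposure, and the sign could be either. It would also be wrong to apply Finland's factors of 0.94–0.83 to the whole pooled RR (1.62–1.43), because Sweden adds no terminations and Norway only later ones.

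The plan has real safeguards. MCA is analysed in Finland and Norway separately, in live births only and by country (section 9.7.6). Section 9.9 promises country-specific prevalences wherever stillbirths enter the numerator or denominator, which covers the composite, and objective 5 stratifies the composite by country. Terminations are themselves compared between cohorts under objective 2, so a difference by exposure would be visible.

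Finally, the Table 6 denominator can be defended as risk per recorded pregnancy. Keeping only TOPFA conditions on a decision made after exposure.

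Most of this stands and limits the claim. It does not close the gap. Country-specific prevalences still contain the non-event terminations, and a separate comparison of terminations shows a possible bias without removing it from the composite RR. No planned analysis gives that RR on another denominator.

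**Conclusion.** The point holds in a limited form. The pooled prevalences of the composite, MCA, stillbirth and defect cases under Table 6 rest on three different country denominators. The country-adjusted RR is sound if non-foetal termination is equally common in both cohorts and biased otherwise. Under the assumed shares, a true RR of 1.72 would appear as about 1.66–1.54 and a null as about 0.96–0.89. If exposed women terminate less often, the RR is inflated instead. These sizes depend on assumed termination shares and country prevalences, so they illustrate scale and do not estimate a bias. Separately, section 9.9 contradicts itself on the three-country MCA denominator, and its MCA analyses are not carried over to the primary composite. Replacing the Table 6 denominator outright is a choice of estimand that the documents do not compel. Prespecifying the alternatives beside it is enough.

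**What to change.** 1. In section 9.9, state that the three-country MCA denominator is births only, with all elective terminations excluded, so that it matches the paragraph that follows.
2. For the composite, prespecify both prevalence and RR, in both primary comparisons (cohort 1 vs 3 and cohort 1 vs 4), beside the Table 6 analysis:
   - (a) Finland and Norway, denominator TOPFA plus births;
   - (b) all three countries on births only, with MCA in births or stillbirth as the event.
3. Also report stillbirth per births.

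**Cost.** A few more model runs and table rows. Prevalences will be slightly higher than the 24/331 feasibility figure, which can be shown alongside. The minimum detectable RR is practically unchanged (1.71–1.72) for births plus TOPFA if the removed share is equal in both cohorts. The Finland–Norway analysis is less precise (about 1.87 under the assumptions above). Analysis (b) still carries the Swedish stillbirth threshold of 28 weeks and the unequal MCA follow-up, so it should also be shown by country.
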